Study Protocol and Statistical Analysis Plan

Title of Study: Effects of Transcutaneous Vagus Nerve Stimulation (taVNS) in Individuals with Primary Dysmenorrhea: A Randomized Controlled Study

NCT Number: NCT06146569

Date of Document: September 18, 2023

Table of contents

	Page number
Study Protocol	3
Objectives	3
Design	3
Methods	3
Statistical Analysis Plan	4

Study Protocol

Objectives:

This study aims to investigate the effects of transcutaneous auricular vagus nerve stimulation (taVNS) on pain, functional and emotional symptoms, and physical performance in individuals with primary dysmenorrhea (PD).

Design:

A small randomized controlled trial design was conducted online at two time points: 1) baseline/pre-test and 2) post-test (one week after pre-test). Data were collected by face-to-face interview method.

Participants will be randomly assigned to one of two conditions: 1) intervention (women received taVNS treatment) or 2) sham (Sham applications were applied using a current-free headset specifically designed for this purpose. Participants observed the device's functionality but supplied no current).

The study was approved by the Artvin Çoruh University Rectorate Scientific Publications Ethics Committee (date: 18/09/2023, procedure number: E-105136) and was by the ethical standards of the World Medical Association (Declaration of Helsinki).

Methods:

Sample and Recruitment. Women who had never given birth before participated in the study. To participate in the research, the following criteria must be met: 1) being diagnosed with PD according to the No. 345 Primary Dysmenorrhea Consensus Guidelines; 2) an NRS score of at least three during menstruation before treatment; 3) being a woman between the ages of 18-40; 4) a regular menstrual cycle of 28 ± 7 days; 5) being nulliparous; 6) no history of brain surgery, tumor, or intracranial metal implantation; 7) No chronic genitourinary infection or alcohol or drug use. Potential participants were invited to study at Artvin Çoruh University through voice announcements and brochures. Following diagnosis with primary dysmenorrhea at Artvin State Hospital, those who met the study's inclusion criteria received treatment at Artvin Çoruh University Physiotherapy Laboratory between November 2023 and January 2024.

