Procedure. The current of taVNS was applied bilaterally from the tragus and turbinate parts of the ear with the VagustimTM device. The current frequency used in modulation mode is 10 Hz, and the pulse width was 300 μ s (In modulation mode, the pulse rate and width are automatically changed in a loop pattern. The pulse width was reduced by 50% from its original setting in 0.5 seconds; then, the pulse rate was changed in 0.5 seconds, reduced by 50% from the original setting. Total cycle time is 1 second.). The current intensity was applied for 5 minutes, keeping the current constant where the participant felt comfortable. Sham applications were applied using a current-free headset specifically designed for this purpose. Participants observed the device's functionality but supplied no current.

Measures.

Numerical Rating Scale (NRS). Data was queried separately for lower abdominal, waist, and bilateral thigh pain. Participants were required to complete an NRS questionnaire through the Google Forms web survey platform (Google LLC, Mountain View, CA, USA) before bed at

night on days 1, 2, and 3 of two consecutive menstrual cycles. The questionnaire was based on the most severe pain they experienced during the day. The minimum score of the NRS is 0, and the maximum score is 10. Higher scores are associated with more severe pain intensity.

Pressure Pain Threshold (PPT). Fabrication Enterprises, Inc., used a Push-Pull Force Gauge® (1200-304) to measure the pressure pain threshold. This handheld algometer allows linear force application ranging between 0 and 10 kg (22 lb × ¼ lb and 10 kg × 100 g). Initially, two exercises were performed on the dominant forearm's extensor muscles to familiarize patients with the equipment. The evaluator positioned the algometer perpendicular to each point and applied gradual pressure at a constant rate of approximately 0.5 kg/cm²/s. The pressure was increased until the participant reported feeling pain. Each point was evaluated three times, and the average value was recorded. The measurement was performed on five reference points in the abdomen and one reference point in the lumbar spine, as in a previous study where pain was evaluated in PD.

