Menstrual Symptom Questionnaire (MSQ). The scale consists of 22 items and uses a 5-point Likert-type format. Participants were asked to rate the severity of their menstrual symptoms on a scale of 1 (never) to 5 (always). The scale contains three subscales: 'Negative Effects/Somatic Complaints' (items 1-13), 'Menstrual Pain Symptoms' (items 14-19), and 'Coping Methods' (items 20-22). The maximum score on the scale is 110, and the minimum score is 22. MSQ score is calculated by taking the average score of all items in the scale. High scores are associated with increased menstrual symptoms.

Functional and Emotional Measure of Dysmenorrhea (FEMD). Scale consisting of 14 items, evaluates dysmenorrhea functionally and emotionally with a 5-point Likert-type item. The reliability and validity study of the scale developed in 2012. As the scores obtained from the scale with a minimum score of 14 and a maximum score of 70 increase, the functional and emotional impact of dysmenorrhea also increases.

Hamilton Anxiety Scale (HAM-A). Patients with chronic pain often experience mood disorders, such as depression and anxiety. The Hamilton Anxiety Scale (HAM-A) was used to assess the intensity of anxiety symptoms. The scale measures both mental and physical anxiety with 14 symptom-defined items. Each item is scored from 0 (not present) to 4 (severe). The total score range is 0-56. On the anxiety scale, scores of 17 or below indicate mild anxiety, while scores of 18-24 indicate moderate anxiety, and scores of 25-30 indicate severe anxiety.

6-Minute Walk Test (6MWT). The 6-Minute Walk Test (6MWT) was evaluated submaximal functional capacity. 6MWT measures the maximum distance participants can walk as quickly as possible for six minutes.

Positive and Negative Affect Schedule (PANAS). For taVNS administration, the positive and negative affect was assessed before and after treatment using the Positive and Negative Affect Schedule (PANAS). This 5-point Likert-type scale was developed in 1988 and includes 20 items: 10 positive and ten negative. A score range of 10-50 assesses both positive and negative effects.

Statistical Analysis Plan

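### The criteria do not screen for contraindications to ear stimulation beyond brain surgery, tumor and intracranial metal, so a woman with a pacemaker meets every criterion as written

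*Combined protocol and SAP*

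**What the plan says.** The Sample and Recruitment paragraph (Study Protocol, Methods) introduces its list with "To participate in the research, the following criteria must be met" and gives seven items. Items 1 to 5 cover the diagnosis, a minimum pain score, age 18-40, cycle regularity and nulliparity. Item 6 is "no history of brain surgery, tumor, or intracranial metal implantation". Item 7 is "No chronic genitourinary infection or alcohol or drug use". There is no separate exclusion list.

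The same paragraph says how a candidate reaches treatment. After diagnosis at the hospital, "those who met the study's inclusion criteria received treatment at Artvin Çoruh University Physiotherapy Laboratory".

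The Procedure paragraph states that "The current of taVNS was applied bilaterally from the tragus and turbinate parts of the ear". Intensity is held at a level comfortable for the participant, for 5 minutes. The sham headset carries no current.

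**The concern.** Including criterion 6 implies that the authors saw a need to screen for conditions that might make electrical stimulation unsuitable. The screen stops at brain surgery, tumor and metal inside the skull. The stimulation is applied to the outer ear, and its intended target is the vagus nerve, whose involvement in heart-rate control is general physiology. Three topics therefore seem natural to ask about: implanted electronic devices outside the skull, known heart-rhythm disorders, and the condition of the ear and skin where the electrodes sit. The plan asks about none of them.

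What is at stake is the safety of an individual participant in the active arm. The analysis is not affected. Eligibility also carries more weight than usual here, because the plan describes no later safeguard: the listed measures include neither heart-rate monitoring nor collection of adverse events.

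**Working it through.** The plan states no figure on this point, so there is none to reproduce. The check is to apply the criteria, as a site would, to candidates who otherwise qualify (items 1 to 5 met, item 7 met).

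| Candidate | Items 1-5 | Item 6 (brain surgery, tumor, intracranial metal) | Item 7 (infection, alcohol, drugs) | Result as written |
|---|---|---|---|---|
| Has a pacemaker | met | met: the device is outside the skull | met | eligible |
| Known heart-rhythm disorder | met | met: not mentioned | met | eligible |
| Wound or skin disease at the electrode site | met | met: not mentioned | met | eligible |
| Has a cochlear implant | met | unclear: depends on how a site reads the undefined intracranial-metal term | met | ambiguous |

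The next step is to see whether the rest of the document closes the gap.

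- Design: random assignment to taVNS or sham; no safety screen.
- Sample and Recruitment, after the list: diagnosis at the hospital, then treatment for those who met the criteria. No cardiac history, implant question or ear examination is described.
- Procedure: device, site, frequency, pulse width, duration and comfort-based intensity. It does not refer to the manufacturer's contraindications.
- Measures: pain rating, pressure pain threshold, menstrual symptoms, functional and emotional impact, anxiety, walk distance and affect. None is a safety measure.
- Statistical Analysis Plan: nothing on eligibility or safety.

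The first three rows of the table therefore stand. An eligible woman is not certain to receive current, since she may be assigned to sham. What is shown is that the written rule admits her, not that any such woman was enrolled.

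**The case against.** The strongest reply is that the omission can be verified but the harm cannot. The documents say nothing about cardiac effects, device labelling or contraindications. Exposure is limited by a 5-minute application at a comfortable intensity. That does not establish safety, but a fair account has to mention it. This objection stands against any claim about how large the risk is. It does not answer the fact that no screen is written down.

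A reader might infer several stronger things that the documents do not support.

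- *That the chance of enrolling such a woman can be quantified and is substantial.* With an assumed prevalence of 0.5-2% and an assumed 40 participants (the SAP says only that n is below 50), 1 − 0.995^40 = 0.18 and 1 − 0.98^40 = 0.55. Those figures count both arms, although only the active arm receives current. With 20 stimulated women, if allocation is 1:1 (no ratio is stated), 1 − 0.995^20 = 0.095 and 1 − 0.98^20 = 0.33. Both ranges rest on an invented prevalence that pools very different conditions, so neither is evidence about this trial.
- *That criterion 6 looks at the wrong part of the body.* The ears are on the head, and asking about intracranial metal is relevant. The list is incomplete rather than misdirected.
- *That a woman with any ear implant is clearly eligible.* A site could exclude a cochlear implant under criterion 6. Likewise, the tumor item names no site, so limiting it to the brain is a natural reading and not the literal text.
- *That one serious event would end the trial or defeat its aims.* The plan has no stopping provision, and its objectives include no safety claim.
- *That the walk test adds to the danger.* The plan says "6MWT measures the maximum distance participants can walk as quickly as possible for six minutes", but it also describes the test as submaximal, and nothing in the plan confines it to the active arm.

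Finally, the paragraph reports treatment in the past tense, between November 2023 and January 2024, although the document is dated September 2023. If recruitment is over, an amendment changes nothing for these participants. That is fair, and it turns the remedy into one of disclosure.

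**Conclusion.** The concern holds as a gap in the written eligibility rule. The seven criteria are the only described gate to stimulation, and a woman with a pacemaker, a known heart-rhythm disorder or a condition at the electrode site meets all of them. This is more than missing detail, because applying the list exactly as written would admit her.

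The size of the risk is unknown. The age range of 18-40 makes the conditions likely to be rare; that is an assumption, not a figure from the plan. The conclusion assumes that no screening document exists beyond the one reviewed. Screening may have been done in practice without being recorded here. Nothing suggests that an ineligible or harmed participant was enrolled. The point deserves correction because the remedy costs little and the plan describes no other safeguard.

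**What to change.** Add a criterion to the Sample and Recruitment list that the candidate has no contraindication to the stimulator under the device's own instructions. Check it by history before randomisation, at the hospital visit where primary dysmenorrhea is diagnosed, and record the answer. The topics asked about should include implanted electronic devices, heart rhythm and the electrode site. The investigator's physician should set the actual exclusion list from the device instructions. This review cannot see those instructions and does not propose the list. The intracranial-metal term in criterion 6 should then be defined and reconciled with the list, so that sites treat a cochlear implant consistently.

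If recruitment is complete, the sponsor should report whether candidates were screened for device contraindications and where that is recorded. If they were not, the report should state this as a limitation.

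The cost is a short amendment, a few history questions at a visit that already takes place, and very few extra screen failures. The analysis needs no change.

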IBM SPSS version 28.0 software (IBM Corp., Armonk, NY, USA) was utilised for statistical analysis. Before the statistical analysis, the Shapiro-Wilk normality test was used to assess data distribution because of $n < 50$. Demographic data and clinical baseline variables were compared among the 2 groups by independent samples t-test for continuous variables and a χ^2 test for categorical variables. Continuous variables were expressed as mean \pm standard deviation (SD), while categorical variables were reported as number and frequency. The independent and paired samples t-test was compared to normally distributed variables between two groups. Two-way analysis of variance (ANOVA) was used for multiple comparisons of normally distributed

variables. The effects of stimulation on pain, pressure pain threshold, menstrual symptoms, and physical performance were calculated using a mixed ANOVA, where the dependent variables were pain, pressure pain threshold, menstrual symptom, and physical performance score, and the independent fixed variables were time, stimulation group (taVNS and sham), and interaction term was group vs time. Post hoc comparisons were carried out when appropriate using Bonferroni correction for multiple comparisons. Greenhouse-Geisser correction was applied when the assumption of sphericity was violated. In the F tests, partial eta squared (η^2) was used as an effect size indicator, elucidated as small, 0.01; medium, 0.06; and large, 0.14. In the t-tests, Cohen's d (d) was used as an effect size indicator, elucidated as small, 0.2; medium, 0.5; large, 0.8. A p value of <0.05 was considered statistically significant.

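### The SAP's mixed ANOVA probably drops women with any missing time level, no analysis population or missing-data method is named, and discomfort from current, one possible cause of loss, can occur only in the taVNS arm

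*Combined protocol and SAP*

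**What the plan says.** Methods, Procedure, describes the active treatment: "The current intensity was applied for 5 minutes, keeping the current constant where the participant felt comfortable". For the control arm, "Sham applications were applied using a current-free headset specifically designed for this purpose", and "Participants observed the device's functionality but supplied no current".

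Design gives the time points as "1) baseline/pre-test and 2) post-test (one week after pre-test". Under Measures, NRS pain is entered on a web form at bedtime on days 1 to 3 of two consecutive cycles. An evaluator measures the pressure pain threshold with an algometer, and physical performance is a six-minute walk test.

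The Statistical Analysis Plan says that "IBM SPSS version 28.0 software (IBM Corp., Armonk, NY, USA) was utilised for statistical analysis". The effects of stimulation "were calculated using a mixed ANOVA, where the dependent variables were pain, pressure pain threshold, menstrual symptom, and physical performance score", with time, group and their interaction as terms. It adds that "Greenhouse-Geisser correction was applied when the assumption of sphericity was violated", and it uses partial eta squared as the effect size. The only indication of sample size is that n is below 50.

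Neither part names an analysis population, a missing-data rule or a sensitivity analysis. Neither asks for a record of incomplete stimulation or of reasons for missing outcomes. Stopping, intolerance and withdrawal are not mentioned.

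**The concern.** Two features of the plan combine. First, one possible reason for leaving, discomfort from the current, exists in only one arm. Second, the stated model appears to be a complete-case analysis. A woman who stops attending and has no post-test would be removed, and the groups compared would no longer be those randomised.

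If loss were heavier in the taVNS arm and the lost women did worse than those who stayed, taVNS would look better than it is. If they did better, it would look worse. With fewer than 50 women, a handful can matter. With no requirement to report missing values and reasons by arm, a reader could not tell whether this had happened.

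**Working it through.** The documents state no sample size, loss rate or standard deviation, so there is no planned figure to reproduce. Every size below is an illustration.

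**Step 1: which form of ANOVA.** The software is SPSS, the model is called a mixed ANOVA, sphericity is corrected by Greenhouse-Geisser, and the effect size is partial eta squared. Together these point to the repeated-measures general linear model, which uses only participants with every time level. This is an inference; the plan does not state deletion. With two time levels sphericity cannot be violated, so the correction has work to do only if time has more than two levels. The diary nights are one candidate, but the plan does not define the levels.

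**Step 2: size of bias if loss occurs in taVNS only.** Let p be the fraction of the arm lost and d the amount by which lost women improve less than retained women. Completer mean minus full-arm mean = p × d.

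- p = 0.10, d = 1 NRS point: 0.10 × 1 = 0.10 points.
- p = 0.20, d = 2 NRS points: 0.20 × 2 = 0.40 points.
- With an assumed 24 per arm, 10% to 20% is 2.4 to 4.8 women.

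**Step 3: effect on type I error.** With two time points, the group-by-time test equals a t-test on change scores. Assume 24 per arm, two-sided 0.05, k women lost from taVNS, and a gap of g SD of change. Bias = (k/24) × g and SE = √(1/(24−k) + 1/24). The error rate comes from the noncentral t with 46−k degrees of freedom and noncentrality bias/SE.

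| k lost | Bias (SD), g = 0.5 | Type I error | Bias (SD), g = 1 | Type I error |
|---|---|---|---|---|
| 1 (4%) | 0.02 | 5.1% | 0.04 | 5.2% |
| 2 (8%) | 0.04 | 5.2% | 0.08 | 5.9% |
| 3 (12.5%) | 0.06 | 5.5% | 0.125 | 6.9% |
| 5 (21%) | 0.10 | 6.3% | 0.21 | 10.2% |

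At g = 0 the bias is 0 and the error 5.0% for any k. A 6,000-replicate simulation agrees: 10% loss with g = 1 gives 0.09 SD and 6.7%, and 20% loss gives 0.20 SD and 9.9%. For scale, the difference detectable with 80% power (normal approximation) is (1.960 + 0.842) × √(1/24 + 1/24) = 0.81 SD with no loss, and 0.86 SD with five lost.

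**Step 4: what a likelihood-based mixed model changes.** Simulation with 20,000 replicates, 24 per arm, SD 2 and pre-post correlation 0.5 (all assumed), with loss in taVNS only:

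| Loss pattern | Size of bias, complete case | Size of bias, likelihood |
|---|---|---|
| Unrelated to baseline, p = 0.10, d = 1 | 0.10 | 0.10 |
| Unrelated to baseline, p = 0.20, d = 2 | 0.40 | 0.40 |
| Dependent on baseline only | 0.17 | 0.00 |

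The last row uses log-odds of loss of −1.7 plus 1 per SD of baseline, so about 19% of the arm is lost. The model removes bias when loss is explained by observed values. It does nothing when loss depends on the unseen outcome.

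**Step 5: partial diaries.** If the six nights were the time levels and nights were missed independently with probability q, deletion would remove 1 − (1−q)^6 of women. At q = 0.02 this is 1 − 0.886 = 11%; at q = 0.10 it is 1 − 0.531 = 47%. These miss rates are assumed. A model using all available values keeps these women.

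**The case against.** A reader might infer that the comparison is already biased by one-sided loss. The documents do not support this. It would require women to find the current intolerable, stop, have no post value as a result, and differ in outcome from those who continued; no section shows any of these. Setting intensity at a comfortable level makes stopping for discomfort less likely. The bedtime NRS form is required of all participants with no exception for incomplete stimulation. Sham women can also leave, for other reasons, and would be deleted by the same rule.

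A reader might also see a contradiction between holding the current constant and keeping it comfortable. The plain reading is to find a comfortable level and hold it, which is consistent.

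It is also fair to object that changing the model does not cure the bias that comes to mind first. Step 4 confirms this for loss unrelated to baseline.

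These points remove any claim that bias is present, but they leave the gap in the plan. The web form covers NRS only: the pressure pain threshold and the walk test go into the same ANOVA and need attendance. A lower chance of stopping is not zero. Nothing in the SAP says how a missing value in either arm would be handled.

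**Conclusion.** The point holds as a gap in the specified analysis, not as a demonstrated bias. The stated ANOVA is reasonably inferred to be complete-case, no all-randomised population or missing-data method offsets this, and one cause of loss is confined to taVNS. Any resulting loss could be unequal by arm and could bias the comparison if those women's outcomes differ.

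The size is unknown. Under the assumed inputs it runs from zero (no loss, or loss unrelated to outcome), through 0.04 to 0.08 SD with two of 24 lost, to 0.21 SD and a 10.2% type I error with five lost and a 1 SD gap. It becomes material only with substantial, outcome-related loss. The figure for diary deletion also assumes that the six nights are analysed as separate time levels; if they are averaged first, one missed night need not remove a woman.

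**What to change.** 1. In the SAP, replace the complete-case repeated-measures ANOVA with a likelihood-based linear mixed model with group, time and group-by-time, and small-sample degrees of freedom. Include all randomised women in their assigned group and every available value, including partial diaries. State which measurements are the levels of time.
2. In both arms, ask for the post-test and remaining diary nights whether or not stimulation was completed. This is the main protection against loss related to outcome, because the model cannot supply values that were never collected.
3. Report missing values and their reasons by arm.
4. Add a simple missing-not-at-random sensitivity analysis: shift the values assumed for women with missing outcomes by a range of deltas, and report the delta at which the conclusion changes.

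The cost is a different SPSS procedure (MIXED in place of GLM repeated measures), a short entry for reasons, and slightly more analysis work. The estimated effect may be a little smaller. If data collection has already finished, items 1 and 4 remain feasible, as does item 3 from whatever records exist.

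### NRS pain is scored at three body sites on three days per cycle, but the SAP does not define the one pain score whose test at p<0.05 decides the pain question

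*Combined protocol and SAP*

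**What the plan says.** The NRS paragraph under Methods, Measures states: "Data was queried separately for lower abdominal, waist, and bilateral thigh pain". Each rating is 0 to 10 and is entered at "night on days 1, 2, and 3 of two consecutive menstrual cycles". Within a day the score is defined: "The questionnaire was based on the most severe pain they experienced during the day". Nothing says how the three sites, or the three days, become one value.

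In the Statistical Analysis Plan, "the dependent variables were pain, pressure pain threshold, menstrual symptom, and physical performance score". The model terms are equally brief: "the independent fixed variables were time, stimulation group (taVNS and sham), and interaction term was group vs time". Site is not among them.

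The decision rule is "A p value of <0.05 was considered statistically significant". The only adjustment is "Post hoc comparisons were carried out when appropriate using Bonferroni correction for multiple comparisons".

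Pain is the first outcome listed in the objective, which is to study effects "on pain, functional and emotional symptoms, and physical performance in individuals with primary dysmenorrhea (PD"). No outcome, site or composite is designated as primary.

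**The concern.** The SAP's single pain variable does not match the data as collected, which are at least three scores per woman per night. The most direct way to run the stated model on those data is once per site, which gives three group-by-time tests of pain, each at 0.05. The sites may disagree, for example with an effect at the thigh and none in the lower abdomen. The plan does not say which result would then answer the pain question.

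The gap cannot easily be filled by presuming an average. Where the authors wanted values combined, they wrote the rule: the three readings at each pressure-pain point are averaged, and the MSQ score is the mean of its items. The NRS paragraph has no such sentence. The eligibility criterion of an NRS score of at least three does not name a site either.

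At stake is the meaning of a statement that taVNS reduces menstrual pain. If the score is chosen after the results are known, the nominal error rate does not apply. Naming NRS pain as the primary outcome would not be enough, because site and day would still be open.

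**Working it through.** **No figure to reproduce.** The document gives no sample size, power or family-wise error rate. The only error-rate input is 0.05 per test.

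**Inputs from the document**
- Sites: 3 (4 if left and right thigh are scored apart, which is not stated).
- Days per cycle: 3, so 3 × 3 = 9 site-by-day scores per cycle.
- Alpha: 0.05 per test. Sidedness is not stated; F tests are non-directional, and I take t-tests as two-sided.
- Sample size: only that n is below 50.

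**Assumptions.** One pre and one post value per site, normal change scores, equal arms, and a common correlation ρ between sites. The document does not give ρ, so a range is shown. With two time points the group-by-time F test is equivalent to a two-sample t-test on change scores.

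**1. Independent sites (upper end of the range)**
- Any site significant: 1 − (1 − 0.05)³ = 1 − 0.8574 = 0.1426.
- Any site significant in favour of taVNS: each two-sided 0.05 test has 0.025 in that direction, so 1 − 0.975³ = 0.0731.

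**2. Correlated sites, each tested once.** Two-sided column: 2,000,000 draws of three equicorrelated z tests (ρ = 0.8: simulated t-tests only). Directional column: 40,000 simulated trials per setting with 12, 20 and 24 women per arm (ρ = 0: formula above).

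| ρ | Any site, two-sided (one test: 5%) | Any site favouring taVNS (one test: 2.5%) |
|---|---|---|
| 0 | 14.3% | 7.3% |
| 0.3 | 13.6% | 6.9–7.0% |
| 0.5 | 12.6% | 6.3–6.4% |
| 0.7 | 10.9% | 5.4–5.7% |
| 0.8 | 9.7–10.0% | 4.8–5.1% |
| 0.9 | 8.4% | not simulated |

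A separate t-test simulation at 15, 20 and 24 per arm agrees on the two-sided rate: 12.5–12.6% at ρ = 0.5 and 11.1% at ρ = 0.7.

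As ratios, the directional rate is 4.8/2.5 = 1.9 to 7.0/2.5 = 2.8 times that of a single test (ρ 0.8 to 0.3). The two-sided rate is 8.4/5 = 1.7 to 14.3/5 = 2.9 times (ρ 0.9 to 0).

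**3. If days are also tested separately.** With nine tests, the two-sided rate is 1 − 0.95⁹ = 0.370 if independent, 0.269 at ρ = 0.5 and 0.203 at ρ = 0.7. Nothing in the SAP says this will be done; it shows what the missing day rule leaves open.

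**4. After the fix.** One pre-specified score gives 5%. Bonferroni across three sites (0.05/3 = 0.0167 each) gives 4.9% if independent, 4.5% at ρ = 0.5, 3.9% at ρ = 0.7 and 3.0% at ρ = 0.9. Holm gives the same rates when no site has a true effect, because its first step uses the same threshold.

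**The case against.** **The SAP does not say that the model is fitted once per site.** It lists pain as one dependent variable, and a mean, sum or worst-site score would fit that wording. This stands. A reader might infer that three ANOVAs are planned, or that any one significant site will be taken as success; the document states neither. What it supports is that the score is undefined, so that this route, among others, is open. An intended composite would need to be written down for the same reason.

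**The 8–14% figure overstates the harm described.** A false claim that taVNS reduces pain is directional, and the two-sided rate also counts results favouring sham. This stands too. The directional rate is about 5–7%, which is roughly two to three times the 2.5% for one test but at or only slightly above 5% in absolute terms. Reading 12–14% as the chance of a false claim of benefit would be wrong.

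**The calculation covers one reading of the model.** The Design section gives two time points, but nothing reduces three daily scores to one. The SAP's Greenhouse-Geisser sentence has no role with only two levels of time, so a time factor with more levels is possible. The rates above are therefore conditional on one test per site, and a fix that names only a site would still leave the day open.

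**It is part of a wider gap.** No outcome is primary, and the six pressure-pain points and the other scales are also tested at 0.05. That is true, but a general statement that NRS pain is primary would not resolve the choice of site and day.

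**Bonferroni might be read as covering the sites.** The sentence is confined to post hoc comparisons, and only where appropriate. It is not said to extend across separate site-level models.

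**Conclusion.** The concern holds as a matter of an undefined pain endpoint. Sites and days are recorded separately, no rule combines them, and no adjustment clearly reaches tests across them. The plan therefore permits a pain claim from any one of at least three full-alpha tests without committing to that analysis.

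With one test per site, the cost is a taVNS-favouring false-positive rate of about 5–7% instead of 2.5%, and a two-sided any-site rate of about 8–14% instead of 5%. These figures rest on the assumed correlations (0.8 to 0.3 and 0.9 to 0 respectively), equal arms, normal change scores and one pre and one post value per site. The size is moderate and uncertain. The ambiguity itself does not depend on those assumptions. The point should be fixed, and the fix is cheap.

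**What to change.** Before the data are analysed, add to the SAP:

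1. One deciding pain score per woman per cycle: either one named site (for example lower abdominal) or a defined composite over the sites, plus one rule for days 1 to 3 (for example their mean). Which site or composite is chosen matters less than that it is fixed in advance.
2. The group-by-time contrast of that score, tested at two-sided 0.05, as the basis for the pain conclusion.
3. The status of the other sites: exploratory, with estimates and 95% confidence intervals, or tested in a stated fixed order only if the deciding score is significant.
4. If all three sites are to count, Holm across the three group-by-time tests, using the same day rule at each site. The Bonferroni step stays for post hoc comparisons.

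The cost is SAP wording only, with no new data or participants. The downside is that an isolated result at another site could no longer carry the pain claim or, under Holm, would face a stricter threshold.

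Timing matters. The document is dated before the treatment period it describes but is written largely in the past tense. If the data have already been seen, a choice of site, composite or day rule must be labelled post hoc, and Holm across the three sites should be used instead of a single chosen score.
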